5.3 Tumor Biopsy (Part B only; optional)

Patients enrolled in Part B will undergo an optional core needle tumor biopsy of the preselected target lesion following completion of baseline metabolic MR scan but prior to initiation of PI3K/mTOR pathway inhibitor. The fresh biopsy sample will be delivered to the [name] lab and will be analyzed for markers of PI3K/mTOR pathway activation, including phosphorylated S6 and Akt, as well as markers of glycolytic activity including LDH expression. When sufficient tissue is available, expression level of MCT1 and MCT 4 (major lactate transporters) will be measured

5.4 Initiation of PI3K/mTOR Pathway-Directed Therapy (Part B Only)

Patients enrolled in Part B will subsequently begin treatment with systemic therapy directed towards the PI3K/mTOR pathway following completion of baseline/screening procedures. Treatment may be given as standard of care with commercial supply (e.g. everolimus) or via participation on therapeutic clinical trial. The study procedures for patients enrolled on a therapeutic trial take precedent over the procedures outlined in the current protocol.

5.5 Day 21 (+/- 14 day) Metabolic MR/HP C-13 Pyruvate study (Part B Only)

Patients will undergo repeat MR scan as per above procedures after 21 days (+/- 14 days) of treatment with androgen signaling inhibitor. Where applicable, patients should take the PI3K/mTOR pathway inhibitor on the day of the MR scan. The target lesion to be evaluated by metabolic MRI will be the same as the prior MR unless lesion has become inevaluable in the interim in the judgment of study investigators. In these cases, an alternate lesion (evaluable baseline MR whenever possible, and adjacent to original target lesion) will be selected for analysis.

5.6 Repeat Tumor Biopsy (Part B Only; Optional)

Patients will undergo optional repeat core needle tumor biopsy following completion of the second MR scan. When possible, patients should remain on PI3K/mTOR pathway inhibitor through the time of the follow up biopsy. The same target lesion will be selected as that biopsied at baseline prior to study initiation whenever possible. In the event that the original target lesion is no longer accessible for repeat tumor biopsy, an alternative metastatic lesion will be selected. Whenever possible, this alternate lesion should be evaluable by metabolic MR imaging.

5.7 Every 6-12 weeks (Part B Only)

Patients will undergo standard disease assessments including standard staging scan every 6-12 weeks per standard of care or per protocol on therapeutic clinical trial. Patients will be followed discontinuation of PI3K/mTOR pathway inhibitor therapy, due to disease progression, unacceptable toxicity, or patient/physician decision to discontinue therapy.

Table 2: Schedule of Study Procedures and Assessments

Period/ Procedure	Screening (28 Days)	Cycle 1 Day 1	Day 21 (+/- 14 days)	Day 28 (+/- 14 days)	Every 6-12 Weeks	Disease Progression
Informed consent	x					
Baseline conditions	х					
AE assessment	х		Х			
Concomitant medications	х		х			
Physical exam	Х					
Vital signs	Х		Х			
Medical history/ Demographics	х					
Tumor Assessment by Standard Scans (within 3 months of C1D1)	Х				X (Part B only)	
Performance status	х					
CBC w/ Diff	х					
Blood chemistry	х					
HP C- 13/metabolic MRI	х		X (Part B only)			
ECG/EKG	х					
		Pai	rt B Only			•
PI3K/mTOR Pathway Inhibitor						
Tumor biopsy (Optional)	Х			х		

5.8 Supportive Care and Concomitant Medications

There are no prohibited medications with hyperpolarized C-13 pyruvate administration.

Subjects should receive full supportive care as medically indicated.

The Principal Investigator or designee will be present during the administration and monitoring period.

Any events occurring during or subsequent to the administration of hyperpolarized C-13 pyruvate will be addressed as required by the monitoring nurse and/or physician as deemed appropriate.

Additional toxicities that arise, including the determination that the injection administered was not sterile, will be treated at the discretion of the treating physician.

A site-specific, radiology tackle-box will be present at the imaging site. This tackle-box contains at a minimum: epinephrine 1mg/1ml, diphenhydramine 50 mg/ml, glucose tablets, NaCl 0.9% 500 ml bag, atropine 1mg/ml, methylprednisolone 125mg/2ml vial, phentolamine 5 mg vial, albuterol 5.5 gram inhaler, sterile water 10ml vial.

6 Reporting and Documentation of Results

6.1 Evaluation of Safety

The study will use the CTCAE v4.0 for reporting of adverse events that occur within 3 days of each imaging procedure and any biopsy-related adverse events.

6.2 Definitions of Adverse Events

6.2.1 Adverse Event

An adverse event (also known as an adverse experience) is defined as any untoward medical occurrence associated with the procedure, whether or not considered related. More specifically, an adverse event (can be any unfavorable and unintended sign (e.g., an abnormal laboratory finding), symptom, or disease temporally associated with the procedure, without any judgment about causality. An adverse event can arise from any use of the procedure.

6.2.2 Adverse reaction

An adverse reaction is defined as any adverse event caused by the procedure. Adverse reactions are a subset of all suspected adverse reactions for which there is reason to conclude that the procedure caused the event.

6.2.2.1 Suspected

A suspected adverse reaction is defined as any adverse event for which there is a reasonable possibility that the procedure caused the adverse event. For the purposes of IND safety reporting, "reasonable possibility" indicates that there is evidence to suggest a causal relationship between the procedure and the adverse event. A suspected adverse reaction implies a lesser degree of certainty about causality than an adverse reaction.

6.2.2.2 Unexpected

An adverse event or suspected adverse reaction is considered *unexpected* if it is not not consistent with the risk information described in the general investigational plan or elsewhere in the protocol. Adverse events that would be anticipated to occur as part of the disease process are considered *unexpected* for the purposes of reporting because they would not be listed in the protocol as being related to the imaging procedure.

6.2.2.3 Serious

An adverse event or suspected adverse reaction is considered *serious* if, in the view of either the investigator or sponsor, it results in any of the following outcomes:

- Death
- Life-threatening adverse event
- Inpatient hospitalization or prolongation of existing hospitalization
- A persistent or significant incapacity or substantial disruption of the ability to conduct normal life function
- Congenital anomaly/birth defect

Important medical events that may not result in death, are life-threatening, or require hospitalization may be considered serious when, based upon appropriate medical judgment, they may jeopardize the patient or subject and may require medical or surgical intervention to

Version date: 10/21/2019

prevent one of the outcomes listed in this definition. Examples of such medical events include allergic bronchospasm requiring intensive treatment in an emergency room or at home, blood dyscrasias or convulsions that do not result in inpatient hospitalization, or the development of drug dependency or drug abuse.

6.2.2.4 Life-threatening

An adverse event or suspected adverse reaction is considered *life-threatening* if, in the view of either the investigator or sponsor, its occurrence places the patient or subject at immediate risk of death. It does not include an adverse event or suspected adverse reaction that, had it occurred in a more severe form, might have caused death.

6.3 Recording of an Adverse Event

All grade 3 and above adverse events will be recorded using the NCI CTCAE v4.0. The Investigator will assign attribution of the possible association of the event with the imaging procedure.

Relationship	Attribution	Description
Unrelated to investigational	Unrelated	The AE is clearly NOT related to the intervention
intervention	Unlikely	The AE is doubtfully related to the intervention
	Possible	The AE may be related to the intervention
Related to investigational intervention	Probable	The AE is likely related to the intervention
	Definite	The AE is clearly related to the intervention

Signs or symptoms reported as adverse events will be graded and recorded by the Investigator according to the CTCAE. When specific adverse events are not listed in the CTCAE they will be graded by the Investigator as *none*, *mild*, *moderate* or *severe* according to the following grades and definitions:

Grade 0 No AE (or within normal limits)
 Grade 1 Mild; asymptomatic or mild symptoms; clinical or diagnostic observations only; intervention not indicated
 Grade 2 Moderate; minimal, local, or noninvasive intervention (e.g., packing, cautery) indicated; limiting age-appropriate instrumental activities of daily living (ADL)
 Grade 3: Severe or medically significant but not immediately life-threatening; hospitalization or prolongation of hospitalization indicated; disabling; limiting self-care ADL
 Grade 4: Life-threatening consequences; urgent intervention indicated
 Grade 5: Death related to AE

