7.7 Interim Analysis

Interim analyses will be conducted for both safety and feasibility. Toxicity will be reviewed on a continuous basis. If at any time (after two or more patients have been accrued) ≥33% of patients experience ≥grade 2 toxicity (excluding asymptomatic laboratory abnormalities deemed to be clinically insignificant by the PI or designee), accrual will be halted for further evaluation.

At the time that it can be determined that continued accrual does not pose significant safety risks to patients accrual may be re-initiated.

Interim analysis for feasibility in Part B will be performed after 33% of patients have been enrolled. Images will be qualitatively reviewed and preliminary data with respect to signal-to-noise ratio within metastatic lesions will be assessed. If it is determined that insufficient signal-to-noise ratio is present to permit analyses of the primary and secondary endpoints, then study accrual will be halted until proper technological adjustments (e.g. alteration of radiofrequency coils, timing from polarization to injection of tracer) have been implemented to ensure higher quality SNR.

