Appendix 2 Data and Safety Monitoring Plan for a Phase 2 or 3 Institutional Study

The UCSF Helen Diller Family Comprehensive Cancer Center (HDFCCC) Data and Safety Monitoring Committee (DSMC) is responsible for monitoring data quality and subject safety for all HDFCCC institutional clinical studies. A summary of DSMC activities for this study include:

- · Review of subject data
- Review of suspected adverse reactions considered "serious"
- Monitoring every six months (depending on study accrual)
- Minimum of a yearly regulatory audit

Monitoring and Reporting Guidelines

Investigators will conduct continuous review of data and subject safety and discuss each subject's treatment at monthly Site Committee meetings. These discussions are documented in the Site Committee meeting minutes. The discussion will include the number of subjects, significant toxicities in accordance with the protocol, and observed responses.

All institutional Phase 2 or 3 studies are designated with a moderate risk assessment. The data is monitored twice per year with twenty percent of the subjects monitored (or at least three subjects if the calculated value is less than three).

Adverse Event Review and Monitoring

All grade(s) 3-5 adverse events, whether or not unexpected, and whether or not considered to be associated with the use of the study drug, will be entered into OnCore®, UCSF's Clinical Trial Management System.

All grade(s) 3-5 adverse events entered into OnCore® will be reviewed on a monthly basis at the Site Committee meetings. The Site Committee will review and discuss the selected toxicity, the toxicity grade, and the attribution of relationship of the adverse event to the administration of the study drug(s).

In addition, all suspected adverse reactions considered "serious" entered into OnCore®, will be reviewed and monitored by the Data and Safety Monitoring Committee on an ongoing basis and discussed at DSMC meetings, which take place every six weeks.

If a death occurs during the treatment phase of the study or within 30 days after the last administration of the study drug(s) and is determined to be related either to the investigational drug or any research related procedure, the Investigator or or the assigned designee must be notified within 1 business day from the participating site(s) and the Study Chair must then notify the DSMC Chair or qualified alternate within 1 business day of knowledge of this event. The contact may be by phone or e-mail.

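### The only stated grade threshold for recording adverse events (grade 3 and above) is higher than what the halting rule counts (grade 2 and above) and what the safety endpoint covers (no threshold)

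*Combined protocol and SAP*

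**What the plan says.** **Recording and entry.** The section on recording, 6.3, begins "All grade 3 and above adverse events will be recorded using the NCI CTCAE v4.0". Appendix 2 uses the same level for the database: "All grade(s) 3-5 adverse events, whether or not unexpected, and whether or not considered to be associated with the use of the study drug" are to be entered into OnCore. It then says "All grade(s) 3-5 adverse events entered into OnCore® will be reviewed on a monthly basis at the Site Committee meetings".

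**Use of the data.** Under 7.7, accrual is halted if (the parenthesis opens just before the quoted words) "after two or more patients have been accrued) ≥33% of patients experience ≥grade 2 toxicity". Clinically insignificant asymptomatic laboratory abnormalities are excluded. The same section says "Toxicity will be reviewed on a continuous basis" but does not say from which record the count is made. Section 7.2 lists adverse event frequency, graded by the Common Toxicity Criteria, as a secondary endpoint and gives no minimum grade. Section 6.1 sets the reporting window at 3 days after each imaging procedure, plus biopsy-related events, again with no minimum grade.

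**Text pointing to wider capture.** After the attribution table, 6.3 adds "Signs or symptoms reported as adverse events will be graded and recorded by the Investigator according to the CTCAE". It also defines grades 1 and 2 for events that CTCAE does not list. Section 6.4 has every adverse event followed to resolution, 7.8.1 brings all data from dosed subjects into the listings and tables, and 8.6 has all study data entered in OnCore. Appendix 2 states "Investigators will conduct continuous review of data and subject safety" and has the monthly meeting discuss "significant toxicities in accordance with the protocol".

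**The concern.** A halting rule needs a data flow that reaches the grade it counts. Here the explicit threshold for recording, database entry and committee review is one grade above the level that triggers the rule. A coordinator who follows the opening sentence of 6.3 and the entry rule of Appendix 2 to the letter would complete every stated requirement without entering a grade 2 event. The rule would then be working on grade 3 and above, although its text says grade 2.

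Grade 2 is not an arbitrary level in this programme. The background section explains that the site's phase I study put its dose-limiting threshold at grade 2 instead of the customary grade 3 because the product is an imaging agent. Section 7.7 uses the same grade. The explicit recording rule does not.

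The safety objective is also exposed. It is meant to extend what is known about the injection's safety profile, and the related toxicity listed so far is almost all grade 1.

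**Working it through.** The plan gives no operating figure for the halting rule or the safety endpoint, so there is nothing to reproduce. The check compares the texts and then counts what a grade 3 threshold would have kept in the sponsor's own earlier data.

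**Step 1. Lowest grade named for each purpose.**

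| Purpose | Section | Lowest grade named |
|---|---|---|
| Recording | 6.3, opening sentence | 3 |
| Recording of reported signs or symptoms | 6.3, later sentence | none |
| OnCore entry | Appendix 2 | 3 |
| Monthly Site Committee review | Appendix 2 | 3 |
| Reporting window | 6.1 | none |
| Halting rule | 7.7 | 2 |
| Safety endpoint | 7.2 | none |

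Wherever a grade is named for recording, entry or monthly review, it is 3. The one use of the data that names a grade names 2. The two sentences in 6.3 do not agree unless the first is read as a minimum only.

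**Step 2. Table 1 of the background section, by grade.** Inputs are the listed possibly, probably or definitely related toxicities, counting the bracketed multiples.

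- 0.14 mL/kg (n = 6): 3 events, all grade 1.
- 0.28 mL/kg (n = 6): 2 events, both grade 1.
- 0.43 mL/kg (n = 19): dizziness 1, dysgeusia 4, fatigue 1, hypocalcemia 1, hypokalemia 1, hypotension 1, nausea 1, headache 1, smell change 2, sore throat 1, giving 14 at grade 1; plus diarrhea 1 at grade 2. Total 15.
- All levels: 3 + 2 + 15 = 20 events in 6 + 6 + 19 = 31 patients. Grade 1: 3 + 2 + 14 = 19. Grade 2: 1. Grade 3 or above: 0.

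**Step 3. What each threshold keeps.**

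| Threshold | All levels | 0.43 mL/kg (the dose in 5.2) |
|---|---|---|
| All grades | 20 of 20 | 15 of 15 |
| Grade 2 and above | 1 of 20 | 1 of 15 |
| Grade 3 and above | 0 of 20 | 0 of 15 |

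**Step 4. Per patient at 0.43 mL/kg, since 7.7 counts patients.** Grade 2 or above: 1/19 = 5.3% (exact 95% interval 0.1% to 26.0%). Grade 3 or above: 0/19 = 0% (0% to 17.6%). These are rates of related events. Section 7.7 states no attribution limit, so they are not the rate the rule would see.

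No probability of a halt is given, because the documents state no expected rate of grade 2 toxicity for this population.

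**The case against.** The strongest reply is that the opening sentence of 6.3 is a minimum. It does not say that only grade 3 and above is recorded. The later sentence in the same section has reported signs or symptoms graded and recorded without a limit, and the grade 1 and 2 definitions would have little use otherwise. Sections 6.4, 7.8.1 and 8.6 all speak of every event or all data. Appendix 2 looks like institutional text: it is titled for phase 2 or 3 studies and mentions participating sites, although this is a single-center study. Sections 6.1 and 7.2 are merely silent on grade, so the only direct clash is 7.7 against 6.3 and Appendix 2. Continuous review is promised in both 7.7 and Appendix 2.

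Much of this stands. A reader might infer that grade 1-2 events will go unrecorded and that the halting rule cannot work. The documents do not support that, because the all-grade reading is available.

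A reader might also infer that events arising after the 30-minute check in 5.2 would be lost. That depends on the contact schedule, not on grade: a late grade 3 event would face the same position. Table 2 places adverse event assessment in both columns that contain a scan, and the only events the background text dates to the day after injection were grade 1. It forms no part of this point.

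The reply does not remove the mismatch. A stated minimum of grade 3 still does not require the grade 2 data that 7.7 uses. The general sentence in 8.6 does not settle whether a grade 2 event is study data, and institutional wording still governs entry once it is an appendix to the protocol.

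**Conclusion.** The inconsistency is real and should be fixed, but its consequence is conditional. What the documents establish is that the only grade threshold stated for recording, OnCore entry and monthly review is above what 7.7 counts and what 7.2 covers, and that 6.3 supports two readings.

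If the grade 3 threshold is applied literally, the 7.7 count would lack grade 2 events. On a Table 1 pattern, the 7.2 table would hold none of the related toxicity: 0 of 20 events overall and 0 of 15 at 0.43 mL/kg. If the all-grade reading is applied, nothing is lost.

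The size rests on three limits. Table 1 lists related events only. Its single grade 2 event was thought more likely due to the enema given for the endorectal coil. And 31 men with localized prostate cancer may not represent patients with advanced solid tumors. The mismatch between the sections does not depend on any of these.

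**What to change.** Reconcile 6.1, 6.3, 7.2, 7.7 and Appendix 2 in one statement:

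- Adverse events in the 6.1 window (within 3 days of each imaging procedure, plus biopsy-related events) are recorded and entered in OnCore with attribution.
- Recording and entry reach at least the grade that 7.7 counts, and cover all grades for the 7.2 endpoint.
- That record is named as the source for both the 7.7 count and the 7.2 safety table.

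The halting threshold itself is unchanged.

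The cost is wording in the listed sections and a few more CRF lines per scan. The downside falls in Part B: around the day 21 scan the window will also collect low-grade events from the PI3K/mTOR inhibitor, so attribution has to be completed for them.

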6.4 Follow-up of Adverse Events

All adverse events will be followed with appropriate medical management until resolved. Patients removed from study for unacceptable adverse events will be followed until resolution or stabilization of the adverse event. For selected adverse events for which the imaging procedure was stopped, a second attempt at imaging may be conducted if considered both safe and ethical by the Investigator.

Reporting to the Data and Safety Monitoring Committee

If a death occurs during the treatment phase of the study or within 30 days after the imaging procedure and it is determined to be related either to the study procedure, the Investigator or his/her designee must notify the DSMC Chair (or qualified alternate) within 1 business day of knowledge of the event. The contact may be by phone or e-mail.

Reporting to UCSF Institutional Review Board (IRB)

The Principal Investigator must report events meeting the UCSF IRB definition of "Unanticipated Problem" (UP) within 5 business days of his/her awareness of the event.

7 Statistical Considerations and Image Analysis

7.1 Image Processing and Analysis

For each patient, a target metastatic lesion will be selected on the basis of standard imaging (CT or MRI). A region-of-interest (ROI) will be manually drawn in the target lesion, and the same lesion will be evaluated on serial MR scans if the lesion continues to remain evaluable by MRI. If lesion is no longer evaluable on follow up scan, an alternative lesion will be selected on the basis of proximity to original lesion and accessibility by radiofrequency coil for purposes of metabolic MR evaluation.

For the analysis and interpretation of the HP ¹³C MR imaging data, we will utilize the opensource DICOM software package (SIVIC) to align, display and quantitatively interrogate serial multiparametric imaging data. Intra-tumoral ROI will be used to quantify peak HP lactate/pyruvate ratio values in the selected volumes of interest.

In an exploratory fashion, additional metastatic sites in addition to the target lesion will be analyzed and interpreted to determine intra-tumoral peak HP lactate/pyruvate ratio.

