3.3 Eligibility Criteria

Inclusion Criteria:

- Presence of at least one target liver or other intra-abdominal lesion detected by standard staging scans that, in the judgment of Study Investigators, would be amenable to hyperpolarized C-13 pyruvate/metabolic MR imaging:
 - o Target lesion must measure ≥1.0 cm in long axis diameter on CT or MRI
- The subject is able and willing to comply with study procedures and provide signed and dated informed consent.
- Eastern Cooperative Oncology Group (ECOG) Performance Status of 0 or 1 (see Appendix 1).
- Adequate organ function, including creatinine < 1.5 x ULN or estimated creatinine clearance ≥50 mL/min (by the Cockcroft Gault equation) and total bilirubin <3xULN.

Part B only:

- No prior local therapy to target lesion.
- If patient agrees to optional biopsy:
 - Presence of at least one target lesion amenable to percutaneous tumor biopsy in the judgment of Interventional Radiology
 - No history of bleeding diathesis.
 - Patients on anti-coagulation they must be able to safely stop treatment for purposes of tumor biopsy.
- Planned treatment with agent targeting Pl3K/mTOR pathway (either standard of care or investigational agent)

Exclusion Criteria

- Patients who because of age, general medical or psychiatric condition, orphysiologic status cannot give valid informed consent.
- Patients unwilling or unable to undergo MR imaging, including patients with contraindications to MRI, such as cardiac pacemakers or non-compatible intracranial vascular clips.
- Metallic implant or device that distorts local magnetic field and compromises the quality of MR imaging.
- Poorly controlled hypertension, defined as systolic blood pressure at study entry greater than 160 mm Hg or diastolic blood pressure greater than 100 mm Hg. The addition of anti-hypertensives to control blood pressure is allowed.
- Congestive heart failure or New York Heart Association (NYHA) status ≥2.
- A history of clinically significant EKG abnormalities, including QT prolongation (QTcF > 500 ms), a family history of prolonged QT interval syndrome, or myocardial infarction (MI) within 6 months of study entry. Patients with rate-controlled atrial fibrillation/flutter will be allowed on study.
- Any condition that, in the opinion of the Principal Investigator, would impair the patient's ability to comply with study procedures.

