5.2 Metabolic MR Imaging

Pre-Scan Evaluation

Vital signs (systolic and diastolic blood pressure, heart rate) will be monitored at screening and baseline (immediately before the subject is transferred to the MR suite).

Before vital signs are measured, the subject should be resting for at least 5 minutes (if possible). The same position will be used each time vital signs are measured for a given subject and blood pressure will be measured from the arm contra-lateral to the site of IMP administration whenever possible.

Standard MR scanning

Patient is transferred to the MR suite. High spatial resolution MRI to visualize the target lesion using appropriate radiofrequency coil will be performed with axial and coronal T1 and T2 ¹H fast spin echo MRI. Gadolinium contrast will be administered intravenously and contrast-enhanced images will be obtained.

Hyperpolarized C-13 Injection and Dynamic ¹³C MR imaging

Next, hyperpolarized C-13 pyruvate will be injected intravenously at a rate of 5 mL/second followed by a 20 mL saline flush at 5 mL/second.

1-2 minutes post-injection

- Dynamic ¹³C MRI
 - ¹³C 3D MRSI sequence with Multiband spectral-spatial excitation pulse for minimal [1-¹³C]pyruvate saturation and echo-planar spectroscopic imaging (EPSI) readout for accelerated spectral-spatial sampling.
 - $_{\odot}$ The pre-selected target lesion will be imaged on a GE 5T system with parameters typically being T_{E} = 3ms, T_{R} = 125ms, 10 Hz spectral resolution, 581 Hz spectra bandwidth, 8 (PE) x 18 (EPSI) matrix, 5x5 mm resolution, 5mm slice thickness, and 5 s per image. The sequence will be started 5 sec after completing the injection (including catheter flushing) of 250mM HP pyruvate (dose = 0.43 mL/kg, 20 to 45 cc's).
 - A "clamshell" volume ¹³C transmit and/or external RF coils will be used for signal excitation and reception.
 - A second hyperpolarized C-13 injection and dynamic 13-C MRI scan may be performed within 15 to 60 minutes following completion of first scan.. This repeat injection and scan is optional.

Post-injection safety monitoring:

Vital signs (blood pressure and heart rate), adverse event assessment, and injection site monitoring will be performed at 30 minutes post-injection.

Reporting of MR Findings:

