7.2 Study Endpoints

Primary endpoints:

Part A: Signal-to-noise ratio with respect to intra-tumoral hyperpolarized C-13 lac/pyr ratio detected within target liver or other intraabdominal metastasis in patients with advanced solid tumor malignancies.

Part B: Mean percent change from baseline in peak intra-tumoral hyperpolarized lactate/pyruvate ratio after initiation of treatment with PI3K/mTOR pathway inhibitor.

Secondary endpoints

- Frequency of adverse events as graded by Common Toxicity Criteria version 4.0
- Association between percent change from baseline in peak intra-tumoral HP lactate/pyruvate ratio on metabolic MR imaging with subsequent outcomes on PI3K/mTOR pathway inhibitor therapy including clinical benefit rate and progression-free survival (Part B)
- Intra-patient reproducibility of HP lac/pyr ratio for patients who undergo repeated dose imaging studies, as descriptively reported using summary statistics (mean difference, standard deviation, range).

Exploratory endpoint

Association between HP peak lactate/pyruvate signal with immunohistochemical expression level of markers of PI3K/mTOR and glycolytic pathway, including LDH, phosphorylated S6, and phosphorylated Akt. (Part B)

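### Section 7.1 takes the Part B primary endpoint from a hand-drawn ROI without specifying a masked read or defining 'peak', so reader expectation, and possibly lesion size, cannot be separated from drug effect

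*Combined protocol and SAP*

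**What the plan says.** The Part B primary endpoint in section 7.2 is "Mean percent change from baseline in peak intra-tumoral hyperpolarized lactate/pyruvate ratio after initiation of treatment with PI3K/mTOR pathway inhibitor". Section 7.1 gives the measurement: "A region-of-interest (ROI) will be manually drawn in the target lesion", and then "Intra-tumoral ROI will be used to quantify peak HP lactate/pyruvate ratio values in the selected volumes of interest". The software is to "align, display and quantitatively interrogate serial multiparametric imaging data".

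Section 7.1 does not say who draws the ROI, how many readers there are, whether they know the scan date or the patient's outcome, in what order scans are read, or how ROI size is controlled. No other section of the supplied documents says so either. The radiologist review within 24 hours (section 5.2) looks for unexpected clinical findings and is not this measurement.

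Other relevant provisions:

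- **Voxel size** (section 5.2, given as typical): "5x5 mm resolution, 5mm slice thickness".
- **Smallest eligible lesion** (section 3.3): 1.0 cm "in long axis diameter on CT or MRI".
- **Change of lesion** (sections 5.5 and 7.1): the same lesion is followed "unless lesion has become inevaluable in the interim in the judgment of study investigators"; otherwise "an alternative lesion will be selected on the basis of proximity to original lesion and accessibility by radiofrequency coil".
- **Planned effect** (section 7.3): a ratio of 0.80 falling to 0.45.
- **Primary analysis** (section 7.8.2): mean change with a 95% confidence interval, without adjustment for lesion or ROI size.

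**The concern.** Placing a hand-drawn boundary is a judgement. A reader who knows which scan is on treatment, and knows that a fall is expected, can shade that judgement without meaning to. In a before/after comparison with no control group, such shading enters the estimate directly and nothing in the design removes it. The optional same-day repeat scans do not help, because both are taken at the same time point and carry no expectation of change.

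The second issue depends on the word *peak*. The maximum over an ROI depends on how many voxels it holds. With 5 mm voxels and lesions as small as 1 cm, that number is small and changes quickly with diameter. A lesion that shrinks would then show a lower *peak* with no change in metabolism.

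Two results are at stake. One is whether the confidence interval for the primary endpoint excludes zero. The other is the comparison in section 7.8.3 of objective response between groups split at the median percent change: a size-dependent measure would be partly correlated with RECIST response by construction.

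**Working it through.** **1. The plan's own figures.** From section 7.3, (0.80 − 0.45)/0.80 = 43.75%, while the text calls it 35%; hence a yardstick of 35–44%. The stated power above 85% cannot be reproduced because no SD of the paired difference is given. With n = 30, a two-sided 5% test and a fall of 0.35, it holds for any SD up to 0.618. This point does not dispute that figure.

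**2. Reader expectation.** Set side by side, the plan has a manual ROI (7.1), serial data aligned and displayed together (7.1), an expected fall (7.3), no control group, and no masking or read-order rule. The size of any resulting bias cannot be computed from the documents.

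**3. Lesion size, if *peak* is the highest voxel.**

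Inputs from the documents: voxel volume 0.5 × 0.5 × 0.5 cm = 0.125 cm³ (5.2); minimum diameter 1.0 cm (3.3). Assumptions: spherical lesions; independent, normally distributed voxel values with a coefficient of variation (cv) of 10–30%; true ratio unchanged.

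- Voxel count: n = (π/6) × D³ / 0.125, giving 4.19 at 1 cm, 33.5 at 2 cm and 113.1 at 3 cm.
- A 30% fall in diameter multiplies n by 0.7³ = 0.343, giving 1.44, 11.5 and 38.8.
- Expected maximum of n standard normals: E(n) = ∫ x·n·φ(x)·Φ(x)^(n−1) dx, which also accepts non-integer n.
- Relative change = (1 + cv·E(n₂)) / (1 + cv·E(n₁)) − 1.

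Example, 1 cm lesion with a 30% fall: E(4.19) = 1.058 and E(1.44) = 0.309. At cv = 0.1, 1.0309/1.1058 − 1 = −6.8%. At cv = 0.3, 1.0927/1.3174 − 1 = −17.0%.

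| Diameter change | 1 cm | 2 cm | 3 cm |
|---|---|---|---|
| −30% | −6.8% to −17.0% | −4.0% to −8.9% | −3.2% to −6.9% |
| −10% | −1.8% to −4.5% | −1.1% to −2.5% | −0.9% to −1.9% |
| +20% | +2.8% to +7.1% | +1.8% to +4.0% | +1.5% to +3.2% |

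**4. What a shift of this order does to the test.** Take n = 30, a true change of zero, and an assumed SD of percent change of 20 to 60 points. The chance that the two-sided 95% interval lies wholly below zero comes from the noncentral t with 29 degrees of freedom and noncentrality (bias/SD) × √30.

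- Average bias of −5 points: noncentrality 1.37 (SD 20) to 0.46 (SD 60) in absolute value; chance 26% to 6%.
- Average bias of −10 points: noncentrality 2.74 to 0.91; chance 75% to 14%.

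Without bias the chance is 2.5%. These are averages over the whole cohort. In the table, a 10% fall in diameter never reaches 5 points, so voxel count alone would do this only if many lesions were small or shrank considerably. A reader effect of the same size would act in the same way.

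**The case against.** The strongest objections, and what stands of each:

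- **The documents do not say the reader is unmasked.** A reader of section 7.1 might infer that. The text is silent, and silence does not show how the reads are done. This stands. The defect is that nothing requires a masked read.
- ***Peak* may mean peak over time.** Section 5.2 describes a dynamic acquisition with an image every 5 seconds, so this reading is at least as natural. If it means the highest point over time of an ROI average, the voxel-count mechanism disappears. This stands, and it makes step 3 conditional. It does not touch the masking point.
- **The shrinkage scenario is severe.** The second scan comes at day 21 ± 14, and section 1.2 reports that preclinical ratio declines preceded any change in tumour size. A 1 cm lesion that loses 30% might be judged inevaluable and replaced. This stands for the larger figures, which is why the 10% case is also shown.
- **The effect is not one-directional.** A reader might infer that it always favours a decline. Growing lesions gain, and some of these patients will progress, so the net direction over 30 patients is unknown. This stands.
- **The noise inputs are not in the documents.** True. Independence between voxels is also an assumption, and positive correlation between them would reduce the effect.
- **The study is exploratory**, its primary analysis is descriptive, and the scans do not guide care. This limits the consequences but does not offset a remedy that costs so little.

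**Conclusion.** The point holds in this form. The Part B primary endpoint depends on a manual ROI and an undefined *peak*, with no masking or read order specified, in an uncontrolled before/after comparison that expects a fall. Reader expectation therefore cannot be separated from drug effect, and its size is unknown.

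If *peak* is the highest voxel, lesion size adds a second influence: about −7% to −17% (1 cm), −4% to −9% (2 cm) and −3% to −7% (3 cm) for a 30% fall in diameter, about −1% to −5% for a 10% fall, and increases with growth. These figures rest on spherical lesions, independent normal voxels and 10–30% noise.

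It would be tempting to conclude that shrinkage could produce the planned decline by itself. These figures do not support that, since every one is well below 35–44%. Rounding the 1 cm voxel counts to 4 and 1 would give 9–24%, but that overstates what the formula yields from 4.19 and 1.44. What can be said is that a shift of this order can move the 95% confidence interval and, on the highest-voxel reading, could create part of any association between ratio change and RECIST response.

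**What to change.** Amend section 7.1 in three places:

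(a) The same reader draws all ROIs on the proton images already acquired under section 5.2, with date and time point removed, in random order, and before response and progression-free survival data are available. Alignment and serial display follow once the ROIs are fixed.

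(b) State whether *peak* is taken over voxels or over time.

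(c) Add a sensitivity analysis of the primary endpoint using the ROI mean, or a fixed-volume ROI of equal size at both scans.

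This is a cheap improvement. It needs no extra scans, patients or readers; the cost is de-identifying and shuffling files, slightly slower reading and one further calculation on stored images.
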